6.0 Procedures Involved

Describe and explain the study design.

The study uses a between-subjects experimental design. Participants will be randomly assigned to one of two conditions: experimental vs. control.

Research procedures, including procedures being performed to monitor subjects for safety or minimize risks.

The study involves two parts: a pre-session online baseline survey and an experimental session that will take place in the lab. Trained research assistants will guide participants through study procedures in the lab, including delivery of the intervention (manipulation), assessment of study outcomes, and study debriefing.

As identified in our pilot data and previous research,^{5,7-9,46,113} employment is a common setting for weight discrimination. Negative employment outcomes (e.g., lower wages, fewer opportunities for promotion) often stem from negative stereotypes that cast employees with obesity as lazy, unintelligent, and incompetent.^{5,8} To manipulate weight discrimination, this study will adapt manipulations widely used in previous experimental studies of social exclusion (conducted by Co-I [name])^{50,112} and weight stigma,⁴¹ as well as our own pilot work.⁴⁸

The study will be presented as an investigation of "decision making in the workplace," during which participants (adults with obesity) will "interact with" and receive initial impression ratings from three "co-workers" ("confederates," that is, research assistants posing as other participants). Participants will be told that the research team has partnered with the FSU marketing department to study how psychological factors affect decision making and that during the lab session they will work with their groupmates to develop a food product marketing campaign.

To begin, participants will create a 3-minute introductory "getting to know you" (GTKY) video, as in our pilot study.⁴⁸ To guide the creation of their video, participants will be provided with a list of "getting to know you" questions (please see attached video introduction questions) they can answer in their video. Participants will also complete a "getting to know you" questionnaire in which they will be asked to indicate their personal qualities (filler questions that assess self-monitoring practices) and social values where they will be asked to rate their attitudes toward elderly adults, overweight people, and

PROTOCOL TITLE: Decision Making Study

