In the control condition, participants will learn that their group members have positive attitudes toward people with higher body weight, as well as elderly and racial/ethnic minority individuals, as indicated by the GTKY summary ratings handout (control condition). Participants will also receive positive feedback about their personal attributes, as indicated by the summary ratings averaged across the three members (control condition).

After (ostensibly) assembling the group's preferences, the experimenter will inform participants in the experimental condition that no one selected them to be their partner, thus they will perform the next few tasks alone. This manipulation has been shown to prompt feelings of social exclusion.⁵⁰ In contrast, participants in the control condition will be told that one of their group members had to leave unexpectedly for a family emergency, so pairs cannot be assembled as usual, thus they will perform the next few tasks alone. In sum, while participants in both conditions will perform the tasks alone, only those in the experimental condition should experience social exclusion. For the exact wording of the social exclusion manipulation, please see the attached script (social exclusion manipulation).

PROTOCOL TITLE: Decision Making Study

After the manipulation has been delivered, participants will complete a manipulation check (see lab survey). Participants will be asked to indicate their overall impressions of their groupmates and their perception of their groupmates' overall impressions of themselves. Participants will be also report the extent to which they think the impressions their group members formed of them thus far are based on various factors including their gender, race or ethnicity, weight, age, personality, and what they said in their video.⁴⁸

Next, participants will complete primary outcome measures (Table 1). To assess comfort eating, participants will take part in a well-validated faux taste test from previous research (described below).¹⁰² To provide a measure of social avoidance/withdrawal, we will use a previously validated measure⁵⁰ in which participants indicate the extent to which they prefer to complete the final task either by themselves, with a member of their previous group, or with a new partner (described below). Anthropometric measures (i.e., height, weight, waist and hip circumference) will be assessed at the end of the study following standard lab-based procedures.

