To assess social avoidance/withdrawal, the experimenter will say the following after the participant has completed the food tasting task:

“Next, you’ll be sharing your ideas for the food marketing campaign. There are a few ways we can do it and it’s up to you. You can do it by yourself, you can do it with one of the remaining people from your previous group—the same people in the videos you watched earlier—or there’s someone else who showed up late for the study and you could do it with them. You haven’t met them yet, but they’ll be doing the marketing task as well so that’s another option. Just so you know, the task will take the same amount of time whether you do it by yourself or with another person.

So again, your options are by yourself, with a former group member, or with the new group member who showed up late. Please give it some thought. I’ll be back in a few minutes and you can let me know your preference then.”

Participants will be asked to indicate their response verbally to the experimenter, who will record their response.

Describe procedures performed to lessen the probability or magnitude of risks and source records

Our team is highly committed to the protection of participant welfare. We will work closely with our university’s Institutional Review Board to ensure participant wellbeing and safety. Further, we will follow best practices for debriefing all study participants.

We will follow best practices for saliva sample collection. For example, participants will receive verbal instructions from the experimenter along with a written handout that

PROTOCOL TITLE: Decision Making Study

repeats the instructions and provides additional tips if they are having difficulty producing enough saliva (please see attached). Participants will also be given privacy and as much time as needed to provide the sample.

All participants will undergo a “funneled” debriefing process at the end of the study that begins with broad questions that narrow to probe for suspicion. The debriefing process will consist of an initial verbal debriefing with the research assistant, followed by receipt of a written debriefing form that provides additional information and psychological support resources. After receiving this information, participants will have the opportunity to discuss the study with the research assistant and ask questions. Here, we provide a brief summary of the verbal debriefing process and the information contained in the written debriefing form.

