Aim 3 power and analysis. The power to detect a moderating effect of age is similar to continuous moderators described in Aim 2. Defining the effect of a binary moderator as the difference in the standardized effects of intervention associated with the two levels of the moderator, The study provides 88% power for a moderator effect of 0.70.¹²² If the moderator is unbalanced (e.g., 60% of participants are female), then the power to detect a moderator effect of 0.70 is 86%. Power is maintained at 84% when there is a more severe imbalance (e.g., 1/3 Hispanic vs. 2/3 non-Hispanic).

All analyses will use the intent-to-treat data sets, meaning all participants will be included and associated with the experimental condition to which they were assigned. Missing outcomes will be addressed using multiple imputation or marginalization (i.e., maximum likelihood). Based on our pilot work, we anticipate little missing data. If the missingness exceeds 10%, however, we will evaluate the potential for nonignorability by including indicators for missingness throughout our analyses.

Participant privacy and data will be carefully protected. Participant information will be collected using a secure web-based application. The baseline survey will be as brief as possible and will be configured for easy completion on multiple platforms (e.g., cell phone, tablet, laptop). Participants will have the option to skip questions that make them uncomfortable. The experimental session will take place in a private laboratory on campus and will be guided through the study by a research assistant.

Data Security

Procedures to eliminate risks related to breach of confidentiality are as follows: Each participant will be given a unique identifier in the data set which will be stripped of all personal information to protect confidentiality. Data sets used for analysis will contain participant identification numbers but neither names nor any other identifying information. Identification information will be retained by the PI for the duration of the study and stored separately from the responses provided by subjects. Data will be stored in password-protected databases on secure servers, accessible only to project staff. Collaborators will receive data stripped of personal identifiers (de-identified data). To ensure complete confidentiality, access to the “key” linking personal identifiers to

PROTOCOL TITLE: Decision Making Study

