At the end of every experimental session, the research assistant will document whether 1) any problems that occurred during the lab session (e.g., session started late; computer problems; participant could not produce sufficient saliva; participant continued to experience psychological distress after the debriefing procedure), 2) whether the participant indicated that their data should be kept or discarded (and if so, why), and/or 3) if a participant decided to withdraw from the study (and if so, why). **The research assistant will be instructed to inform [name] immediately after the lab session if a participant decides to have their data discarded, if a participant continues to exhibit psychological distress after the debriefing process, or if a participant decides to withdraw from the study.**

In order to assure privacy for participants and to minimize risk, we will be primarily using computer-based data collection procedures. This reduces the number of people who view the data and increases self-disclosure on sensitive topics. Access to the data will be password protected.

Each participant will be given a random unique identifier in the data set that will be stripped of all personal information to protect confidentiality. Data sets used for analysis will contain participant identification numbers but neither names nor other identifying information such as home address. Identification information will be retained by the PI for the duration of the project and stored separately from the responses provided by subjects. Collaborators will receive data stripped of personal identifiers (de-identified data). To ensure complete confidentiality, access to the “key” linking personally identifiable information to the participant’s ID will be restricted to the PI. Reports will not identify individual participants. [name] will oversee the data storage and reporting procedures. De-identified data will be stored into perpetuity. The “key” linking personally identifiable information to the participant’s ID in the data set will be destroyed at the end of the project. Reports will only use aggregated data. All study staff will be trained in security and confidentiality procedures before receiving access to any participant data.

Adverse Events. The PI will review the progress of the project and data being collected to ensure that potential adverse effects are identified, if they occur, and reported to the

PROTOCOL TITLE: Decision Making Study

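### Social withdrawal, one of nine primary outcomes, is answered aloud to an experimenter who knows the arm; a privately marked answer would cheaply reduce the scope for arm-dependent reporting

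*Combined protocol and SAP*

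**What the plan says.** Social withdrawal is listed in Table 1 (section 3.0) among the outcomes that section 6.0 calls primary. Section 17.0 counts nine and tests each at alpha 0.005.

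Section 6.0 sets out the sequence:

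- **Manipulation.** "the experimenter will inform participants in the experimental condition that no one selected them to be their partner". Control participants are instead told that a group member had to leave.
- **In between.** A manipulation check and the taste test, for which the participant is left alone for about 10 minutes.
- **The choice.** The script is delivered by the experimenter: "the experimenter will say the following after the participant has completed the food tasting task". The options are to work alone, with someone from the earlier group, or with a newcomer. The experimenter then leaves, promising to "be back in a few minutes and you can let me know your preference then".
- **Capture.** "Participants will be asked to indicate their response verbally to the experimenter, who will record their response".

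On staffing, section 6.0 gives research assistants the whole session, "including delivery of the intervention (manipulation), assessment of study outcomes, and study debriefing", and section 17.0 says the participant "will be guided through the study by a research assistant". Neither section describes a blinded assessor, a second rater or a recording of this answer.

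**The concern.** The person who hears and writes down the answer knows the arm. One of the three options means rejoining the people who, in the experimental arm only, supposedly declined to work with the participant. Stating a preference about them aloud, to the person who appears to have announced that rejection, is not quite the same social act in the two arms. Some participants might hide a wish to be alone, or overstate it, more in one arm than in the other.

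A difference of that kind would be added to, or taken from, the treatment contrast on a primary outcome. With only the spoken answer on file, the planned ANOVA and covariate-adjusted models could not tell it apart from true withdrawal. The sensible time to limit it is at collection.

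**Working it through.** **What the text establishes**

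1. The experimenter knows the arm, because the two arms are told different things about why they will work alone (6.0).
2. That one individual both delivers the message and takes the answer is implied, not stated: 6.0 uses the same role title for both acts, gives research assistants both duties, and 17.0 speaks of a single assistant.
3. Elsewhere the protocol collects comparable information more privately. The earlier partner preference is marked on paper (6.0). The eating task is done alone in a private room, partly so that participants need not fear the experimenter's judgement (4.0). Section 18.0 says of computer-based capture: "This reduces the number of people who view the data and increases self-disclosure on sensitive topics".

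**How much a shift could matter**

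The documents give no proportion choosing to work alone and no bias size, so there is no plan figure to reproduce for this outcome. The Aim 1 statement of 90% power concerns a standardised mean difference of 0.50. What follows is illustration.

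Inputs from section 17.0: n = 160 per arm; alpha = 0.005 (sidedness is not stated for Aim 1; two-sided assumed, z = 2.807). Assumed: the outcome is scored as alone versus not alone, base rates are 20-50%, and any shift is in one arm only.

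Pooled two-proportion test, with difference D and mean proportion m:

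- SE0 = sqrt(2m(1 - m)/n)
- SE1 = sqrt([p1(1 - p1) + p2(1 - p2)]/n)
- rejection probability ≈ Φ((|D| - 2.807·SE0)/SE1), the opposite tail being negligible for the shifts shown

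*Masking a true 20% versus 35% effect:*

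| Recorded | SE0 | SE1 | (\|D\| - 2.807·SE0)/SE1 | Power |
|---|---|---|---|---|
| 20% vs 35% (no shift) | 0.0499 | 0.0492 | 0.20 | 58% |
| 20% vs 33% (2 points) | 0.0493 | 0.0488 | -0.17 | 43% |
| 20% vs 30% (5 points) | 0.0484 | 0.0481 | -0.75 | 23% |
| 15% vs 30% (5 points in both arms) | 0.0467 | 0.0459 | 0.41 | 66% |

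*Mimicking an effect when there is none (5 points, one arm):*

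| Recorded | SE0 | SE1 | (\|D\| - 2.807·SE0)/SE1 | False-positive rate |
|---|---|---|---|---|
| 50% vs 55% | 0.0558 | 0.0558 | -1.91 | 2.8% |
| 20% vs 25% | 0.0467 | 0.0466 | -1.74 | 4.1% |
| 20% vs 15% | 0.0425 | 0.0424 | -1.63 | 5.1% |

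The nominal rate is 0.5%, so a 5-point shift gives roughly 3-5%. A 2-point shift gives 0.8-1.0%.

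The masking loss depends on the assumed effect. The 20% versus 35% contrast is Cohen's h = 2·asin(√0.35) - 2·asin(√0.20) = 0.34, below the 0.50 used in planning. At h = 0.50, over base rates of 20-50%, a 5-point shift takes power from about 95% to 75-78%.

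**The case against.** The best case for the plan is that both arms get the same script, the same options, the same few minutes alone to decide and the same spoken answer. Any reluctance to say one wants to be alone may be common to both. A common shift is not arm-dependent bias: in the illustration, 5 points off both arms gives 66% power, slightly above the unshifted 58%. This stands. It means a differential is plausible, given that one option involves the supposed rejecters, but it is not shown.

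Three further points stand in part:

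- **Recording.** The experimenter transcribes one of three discrete, scripted options and makes no rating. Recording error is likely small; the concern is mainly how participants report.
- **Timing.** A reader might infer that the answer follows directly on the rejection. It does not: the manipulation check and the taste test come between.
- **Computer capture.** A reader might see a contradiction with section 18.0. There is none: that sentence sits in a privacy provision, computer capture is described there as the primary method rather than the only one, and section 6.0 openly plans experimenter-administered questions as well.

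It can also be said that telling the experimenter how to proceed suits the cover story, and that a form might raise suspicion. This is weak, because participants have already marked a partner preference on paper earlier in the same session.

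**Conclusion.** The point holds as a modest one about how the outcome is collected. A primary outcome is spoken to, and written down by, staff who know the arm and who by implication delivered the exclusion message, so reporting could differ by arm.

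Two stronger conclusions are tempting and unsupported. One is that the trial will lose power, or gain false positives, by the amounts above. Those figures rest on assumed rates, an assumed scoring and an assumed one-arm shift, and neither direction nor size can be derived from the documents. They show only that at alpha 0.005 a shift of a few points would be enough to matter. The other is that a private form would eliminate the problem. Unblinded staff would still read the options aloud, so experimenter influence would be reduced, not removed.

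The attached scripts and lab survey were not available for this review, but section 6.0 is explicit that the answer is verbal.

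**What to change.** In the social-withdrawal procedure of section 6.0, keep the script and the experimenter's absence, and replace the verbal response with a choice that the participant marks privately during that absence. A paper slip, as already used for the earlier partner preference, or an item in the lab survey would both serve. Word it to fit the marketing cover story. Showing the options on screen as well would narrow the remaining channel, but the main change does not depend on it.

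The same edit is a chance to settle the response format. Section 4.0 describes the extent of a preference, while the section 6.0 script collects one choice among three; state which is intended and how it will be scored for analysis.

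Cost: one form or survey item, its wording, and a minor IRB amendment. Sample size does not change.

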7.0 Data and Specimen Banking

N/A

8.0 Sharing of Results with Subjects

N/A

9.0 Study Timelines

The duration of an individual subject's participation in the study is a total of 135-140 minutes (15-20 minutes for the baseline survey; 120 minutes for the lab-based portion of the study).

We are aiming to recruit approximately 36 participants per month and will be recruiting for a 9 to 11-month period. If are not able to meet our recruitment goals, we will extend the recruitment window as necessary.

Our estimated date of completion is 9/30/2023. If we need more time to complete the study, we will request a no-cost extension.

10.0 Inclusion and Exclusion Criteria

Interested participants will be directed to an online screening survey via a link or QR code to assess eligibility criteria.

Eligibility criteria: (1) $BMI \geq 30 \text{ kg/m}^2$ (BMI criteria for obesity), (2) ≥ 18 years of age, (3) able to read and understand English, (4) have Internet access (to complete the baseline survey), and (5) able to come to FSU's campus to take part in a lab-based study.

Exclusion criteria: (1) having participated in any of our pilot studies on weight stigma, (2) diagnosed with a current major psychiatric disorder (e.g., major depressive disorder, eating disorder), (3) pregnant or nursing, diagnosed with Cushing syndrome, taking steroid-based medications, or (4) having allergies to ingredients in the foods being offered during the taste test (e.g., gluten, peanuts).

PROTOCOL TITLE: Decision Making Study

We will not be recruiting special populations (adults unable to consent, individuals who are not yet adults, pregnant women or prisoners).

11.0 Vulnerable Populations

N/A

12.0 Local Number of Subjects

Total number of subjects: 320

13.0 Recruitment Methods

Participants will be recruited from the local Tallahassee community and the surrounding area (e.g., Thomasville, Crawfordville). Following procedures used in our pilot work, we will use a variety of recruitment strategies (e.g., flyers, online ads, community outreach). Ads for the study will be distributed in the local Tallahassee community via flyers, online message boards (e.g., Craig's List), and social media sites (e.g., Facebook).

To facilitate recruitment of a racially/ethnically diverse sample, we have partnered with the FSU Center for Translational Behavioral Science's (CTBS) Community Engagement Core. The Community Engagement Core provides community liaison services, consults on engagement methodology, and facilitates the Community Advisory Council. The Council is a community advisory group comprised of area health care providers, professionals, and community members who have come together to enhance CTBS's mission toward effective community engagement in research. The Community Engagement Core is facilitated by [name] and [name] who serve as liaisons between investigators and the Council to engage relevant community partnerships needed to facilitate participant engagement and recruitment. As leaders of local community-based organizations, Council members also provide stakeholder input to facilitate recruitment. Participants will be recruited via direct outreach to locations such as local churches and community-based organizations.

Interested participants will be directed to an online screening survey to assess eligibility criteria.

The ads will provide a brief description of the study and the location where the study will take place. The ads will also mention that study participants will be compensated. Ads will include a link or QR code for the screening survey. Copies of the screening survey and advertisements are attached.

Participants will receive \$75 cash upon completion of the lab-portion of the study.

